#### 5.10.2.2 Assessment

##### 5.10.2.2.1 Method of Assessment

The Sn-117m-DTPA palliative pain effect will be measured by using a pain index as described in the table below (Nilsson *et al.*, 2012).

#### Classification of pain index based on diary pain intensity rating and analgesic intake

Pain response	Pain index	Diary pain rating change from baseline	Analgesic intake compared with baseline
Complete	1	Decrease $\geq 90\%$	Stable or reduced
Marked	2	Decrease $\geq 50\%$ to $< 90\%$	Stable or reduced
Moderate	3	Decrease $> 33\%$ to $< 50\%$	Stable or reduced
Minimal	4	Decrease $\geq 20\%$ or increase $< 33\%$	Stable
None	5	Decrease $< 20\%$ or increase $> 33\%$	Stable

Pain progression	6	Increase $\geq 20\%$	Stable or increased
		Decrease $<20\%$ or increase $<20\%$	Increased
		Decrease $\geq 20\%$	Increased

This pain index is derived from a combination of the following 11-point pain intensity scale and analgesic consumption categorized according to the World Health Organization (WHO) analgesic ladder.

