### 9. STATISTICAL CONSIDERATIONS

#### 9.1 Study Design/Endpoints

This is a single-arm, open-label phase 2 study to evaluate the efficacy of Sn-117m-DTPA on

sustained pain response in patients with CRPC metastatic to at least two bone sites, with at least one clinically meaningful pain at baseline ( $\geq 4$  on an 11-point pain intensity scale). Sustained pain-response is defined as: 1) achieving pain index  $\leq 3$  within a 12-week period and 2) maintaining that pain index  $\leq 3$  over a 16-week time period (beginning when the pain index  $\leq 3$  is initially achieved). The maximum duration of follow-up required to declare a patient a responder is 28 weeks, representing a patient who initially achieves pain index  $\leq 3$  toward the end of the 12-week period and is followed for an additional 16 weeks to confirm maintenance of pain index  $\leq 3$ .

Eligible patients will be assigned to receive Sn-117m-DTPA at 20 mCi/70 kg (0.28 mCi/kg) every 8 weeks for two cycles. Treatment will last for 16 weeks with two treatment injections given at 8-week intervals. The study utilizes a mini-max Simon two-stage design to assess anti-tumor activity and pain benefit of Sn-117m-DTPA.

Patients are not allowed to receive external radiation within 12 weeks from the start of treatment administration. If their pain index does not reach  $\leq 3$  after 12 weeks, they are not meeting the primary endpoint, and they can then get external radiation for pain control.

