#### 9.4.5 Duration of Pain Response

The time from the achievement of pain response (pain index  $\leq 3$ ) to the recurrence of pain (pain index  $\geq 4$ ) will be evaluated.

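### The pain index table lets one visit count as both response and recurrence on stable analgesics, and gives no index at all to many visits on reduced analgesics

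*Combined protocol and SAP*

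**What the plan says.** Section 5.10.2.2.1, in the table headed "Classification of pain index based on diary pain intensity rating and analgesic intake", builds the pain index from the percentage change in worst pain and the change in analgesic intake, both against baseline. The index is taken from a cited dose-response study of radium-223.

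- Index 1 needs a decrease of at least 90%.
- Index 2 reads "Decrease $\geq 50\%$ to $< 90" percent.
- Index 3 reads "Decrease $> 33\%$ to $< 50" percent.
- For all three, analgesic intake must be "Stable or reduced".
- Index 4 reads "Decrease $\geq 20\%$ or increase $< 33" percent, with stable analgesics only.
- Index 5 is a decrease below 20% or an increase above 33%, again with stable analgesics only.
- Index 6 is an increase of at least 20% with stable or increased analgesics, or any change with increased analgesics.

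The cut lies between 3 and 4. Section 9.1 requires reaching index 3 or below within 12 weeks and then "maintaining that pain index $\leq 3$ over a 16-week time period". Section 9.4.4 uses the same cut for the overall pain response rate. Section 9.4.5 defines duration of response as "The time from the achievement of pain response (pain index" 3 or below) "to the recurrence of pain (pain index $\geq 4$ ) will be evaluated". I found no rule for a patient who meets two rows, and Sections 9.1 and 9.4.5 do not say how to treat a visit that meets none.

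**The concern.** A classification table that carries the primary endpoint should put each visit in exactly one row. This one fails in two ways that touch the cut between 3 and 4.

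First, index 4 accepts any decrease of 20% or more, which includes every decrease large enough for index 1, 2 or 3. On stable analgesics, response and non-response are then both satisfied.

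Second, reduced analgesics appear only in the rows for index 1 to 3. A patient who cut analgesics and whose pain then came back has no index.

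The first defect needs an unwritten rule before the endpoint can be programmed. The second affects duration of response even under the most natural reading, because recurrence is defined by reaching index 4 or above rather than by ceasing to be at 3 or below. With 25 patients and decisions at 1 versus 2 responders (stage one) and 5 versus 6 (final), visit-level scoring should not be left to the programmer.

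**Working it through.** The plan states no figure on this point, so there is none to reproduce. The check is to apply the rows exactly as written.

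**Inputs.** Row definitions: Section 5.10.2.2.1. Response cut: Sections 1.1.1, 9.1 and 9.4.4. Recurrence cut: Section 9.4.5. Entry score of at least 4: Section 3.1.4. Score range 0 to 10: item 3 of the pain inventory (Appendix D). Analgesic categories (decreased, stable, increased): Section 5.10.2.1.

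**Step 1: logic.** Let B be the baseline score, F the follow-up score, and d = 100 × (B − F)/B the percentage decrease. Rows 1 to 3 together require d > 33 with stable or reduced analgesics. Row 4 is met if d ≥ 20 with stable analgesics. Since d > 33 implies d ≥ 20, every stable-analgesic response also meets row 4. Example: B = 10, F = 4, stable analgesics gives d = 100 × 6/10 = 60, which is index 2 and index 4.

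**Step 2: count on a grid.** Integer baselines 4 to 10 (7 values) and scores 0 to 10 (11 values) give 7 × 11 = 77 pairs per analgesic category.

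| Analgesics | Rows met | Pairs |
|---|---|---|
| Stable | 1 and 4 | 8 |
| Stable | 2 and 4 | 22 |
| Stable | 3 and 4 | 7 |
| Stable | 4 and 6 | 4 |
| Stable | 5 and 6 | 13 |
| Reduced | one of 1 to 3 only | 37 |
| Reduced | none | 40 |

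- Stable responses that also meet row 4: 8 + 22 + 7 = 37 of 37.
- Reduced-analgesic responses that also meet row 4: 0 of 37.
- Reduced analgesics with no row: 77 − 37 = 40. Of these, 6 + 5 + 4 + 3 + 2 + 1 + 0 = 21 are increases (10 − B for each baseline), 7 are no change, and 40 − 21 − 7 = 12 are decreases of 33% or less.
- Overlaps within indices 4 to 6: 4 + 13 = 17.

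The 17 assumes that a 0% change counts as only a decrease or only an increase. If it counts as both, the 7 stable no-change pairs meet rows 4 and 5, giving 17 + 7 = 24. If it counts as neither, the 7 stable and 7 increased no-change pairs also have no row, giving 40 + 14 = 54 empty cells. The 37 and the 40 reduced-analgesic pairs are the same under every coding.

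**Step 3: effect on the endpoints.**

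- *Stable analgesics.* The patient with d = 60 meets the start of response (index 2) and recurrence (index 4) at the same visit. Taken literally, duration is zero.
- *Reduced analgesics.* Take B = 8. A score of 3 gives d = 100 × 5/8 = 62.5, index 2, a response. A later score of 8 (0% change) or 10 (a 25% increase), still on reduced analgesics, meets no row. The visit is not at index 3 or below, so response is not shown as maintained under Section 9.1. It is not at index 4 or above either, so no recurrence is recorded under Section 9.4.5 and duration runs on.
- *Overlaps within 4 to 6.* Both candidate indices are non-response and both count as recurrence, so no endpoint changes.

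**Step 4: test of the fix.** Capping the row 4 decrease at 33% takes the overlap across the cut from 37 pairs to 0. A rule assigning the lowest index met keeps all 37 as responders without changing the row. Neither change fills the 40 empty pairs.

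**The case against.** The best defence is that the table excludes the harmful reading. If row 4 overrode rows 1 to 3, nobody on stable analgesics could score 1, 2 or 3, and the word stable in those rows would have no function. The rows run in order from Complete to Pain progression, and a 60% decrease inside the bounded Marked row cannot sensibly be Minimal. This stands. A reader might infer that the overlap reverses the primary result or destroys the power of the design. The documents do not support that: it needs row 4 to take precedence, and nothing in the plan suggests it.

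It is also fair that the 17 overlaps and 40 empty cells involve no decrease above 33%, so none can create a response. The grid maps the rule rather than estimating patients, since baseline is a weekly average (Section 3.1.4) and need not be an integer. The published source might bound row 4 or state a precedence rule, but it is not part of the plan.

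The defence does not cover everything. Reading for the best row sends all 17 stable overlaps to index 4 or 5, so on the grid the stable limb of row 6 is never used. The implied rule therefore does not make every row work. Nor does it give an index to reduced-analgesic visits with no row, which is where duration of response goes wrong.

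**Conclusion.** The table is defective as written and should be corrected, but the defect is one of definition rather than a threat to the primary conclusion.

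- On stable analgesics, all 37 response pairs also meet index 4, with no written precedence. The primary responder set is probably recoverable from the row order. The literal clash is with Section 9.4.5, where response and recurrence coincide.
- On reduced analgesics, 40 of 77 pairs have no index. This survives the natural reading. Recurrence can go unrecorded, so duration is overstated for such a patient, and sustained response and duration can disagree.
- Overlaps within indices 4 to 6 affect no endpoint.

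The counts assume integer baselines of 4 to 10 and the rows applied literally, so that one third (for example 6 to 4) counts as more than 33%. How many patients will fall in these cells cannot be judged from the documents.

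**What to change.** Make these changes before any interim scoring:

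1. Cap the index 4 decrease at 33%, where index 3 begins, or state that the lowest index met is assigned.
2. Assign reduced analgesics with a decrease of 33% or less, no change or any increase to a non-response index. Alternatively, define recurrence in Section 9.4.5 as no longer meeting index 3 or below.
3. Check the rows for index 5 and 6 against the cited source, make them non-overlapping, and say how a 0% change is classified. This is for consistency only.

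The sponsor should confirm the 33% cap against the source, because it is inferred from where index 3 starts. The cost is protocol wording, with no new data, visits or patients.

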### Pain intensity scale (Item #3 on the BPI-SF, worst pain)

3. Please rate your pain by marking the box beside the number that best describes your pain at its **worst** in the last 24 hours.

## **Analgesic Use/Consumption**

PATIENT-REPORTED ANALGESIC LOG		
Decrease	Stable	Increase

Both narcotic and non-narcotic analgesic use and pain intensity scales will be captured using the Mediidata Patient Cloud where patients will be able to complete the submission of their worst pain score and analgesic log electronically. A paper format option is allowable in case a digital collection format is not available or the patient is not comfortable using the app (Appendix E). Clinical research coordinators will verify the medication and fill out the pain medication list (Appendix F) with every clinic visit.

### 5.10.2.2.2 Timing of Assessment

Pain at baseline and analgesic use (pre-treatment, Week 0) will be measured via serial (daily) assessments in a 7-day run-in period. Patients will be considered evaluable if they complete assessments on  $\geq 4$  days within the 7-day run-in period. During treatment, pain and analgesic use will be measured every 2 weeks through Week 28, followed by routine clinic follow-up until 1 year or when patients experience new pain. Complete pain assessments via the full BPI-SF (Appendix D) will be collected at baseline, after Cycle 1, after Cycle 2, and at Week 28. Pain assessments will be halted at the patient's request or if the patient discontinues study treatment for reasons other than disease progression.

### 5.10.2.3 Data Recording

### 5.10.2.3.1 Method of Recording

- Pain assessments and analgesic logs will be post-processed using Medidata Rave EDC (electronic data capture). Data collection for this study will be done through Medidata

Rave.

#### 5.10.2.3.2 Timing of Recording

- The pain score and analgesic data will be assessed for inclusion determination during the pre-screening period within 2 weeks of a patient's enrollment.

## 6. TREATMENT PLAN

### 6.1 Agent Administration

Treatment will be administered on an outpatient basis. Reported adverse events and potential risks are described in Section 10. Appropriate dose modifications are described in Section 7. No investigational or commercial agents or therapies other than those described in Sections 6.1 and 6.3 may be administered with the intent to treat the patient's malignancy.

Study Regimen Description				
Agent	Dose	Route	Schedule	Cycle Length
Sn-117m-DTPA	20 mCi/70 kg (0.28 mCi/kg)	Slow IV injection over 10 min	Day 1	8 weeks*

\*Treatment continues for 2 cycles.

**Retreatment** after 2 cycles is allowed after an evaluation of AEs if:

- pain ( $\geq 4$  on 11-point intensity scale) recurs within 6 months after a 16-week pain observation period  
AND
- no disease progression on bone scans ( $\leq 2$  new bone lesions), or evidence of clinical progression (such as development of cancer-related symptoms)

Patients will be administered two additional cycles (8 weeks apart) if they meet the retreatment criteria. The maximum treatment dose per patient is four injections in this study.

Patients will be instructed to maintain a high fluid intake (drink at least two to three quarts of fluid every 24 hours) for 2 weeks after each Sn-117m-DTPA treatment to minimize a concentrated radioactive excretion. In general, drinking alcoholic beverages should be kept to a minimum or avoided completely. Patients will be educated on hygiene instruction/precautions on post-therapy treatment (see Appendix I).

Required Criteria for Each Re-Treatment:

Patients must have adequate organ and marrow function as defined below to be eligible for subsequent treatments after the first treatment administration:

- leukocytes	$\geq 2,000/\text{mcL}$
- absolute neutrophil count	$\geq 1,000/\text{mcL}$
- platelets	$\geq 75,000/\text{mcL}$
- hemoglobin	$\geq 8.0 \text{ g/dL}$
- total bilirubin	$\leq 2.5 \times \text{institutional ULN}$
- AST(SGOT)/ALT(SGPT)	$\leq 5 \times \text{institutional ULN}$
- creatinine*	$\leq 1.7 \text{ mg/dL}$
	OR
- glomerular filtration rate (GFR)	$\geq 50 \text{ mL/min}/1.73 \text{ m}^2$ (see Appendix B)

\*Should a 40% increase over the baseline serum creatinine value occur during the course of treatment, with a concomitant decrease of over 40% in creatinine clearance as calculated from serum creatinine concentrations according to Cockcroft's method (see Appendix B), patients must also have a measured creatinine clearance (or GFR) performed, unless resolved within 16 weeks.

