#### 9.4.8 Clinical Progression-Free Survival

Clinical PFS will be calculated from the time of study enrollment until disease progression, which is defined as 1) symptomatic progression (increasing pain from a metastatic lesion); 2) progression of bone lesions assessed per PCWG3 criteria; or 3) progression of soft-tissue lesions

assessed per RECIST v1.1 criteria. PSA progression without progression on bone lesions nor symptomatic is not considered as clinical progression. Clinical PFS will be censored if clinical progression is not observed.

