## 12. MEASUREMENT OF EFFECT AND DISEASE PROGRESSION

### 12.1 Antitumor Effect – Bone and PSA Response Parameters

#### 12.1.1 Prostate Cancer Working Group 3 (PCWG3) Criteria

The sections of the PCWG3 Criteria that apply to this trial are the criteria for PSA response and progression, and the criteria for bone lesion (non-target) “prevent/delay end points (progression),” described in the table below. See Scher *et al.* (2016) for more details.

Variable	PCWG3 (2016)
PSA	

○ Recognize that a favorable effect on PSA may be delayed for 12 weeks or more, even for a cytotoxic drug

○ Monitor PSA by cycle but plan to continue through early rises for a minimum for 12 weeks unless other evidence of progression

○ Ignore early rises (prior to 12 weeks) in determining PSA response

 
Decline from baseline:
 

○ Record time from start of therapy to first PSA increase that is <math>\geq 25\%</math> and <math>\geq 2</math> ng/mL above the nadir, and which is confirmed by a second value 3 or more weeks later (i.e., a confirmed rising trend)

 
No decline from baseline:
 

○ PSA progression <math>\geq 25\%</math> and <math>\geq 2</math> ng/mL after 12 weeks

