Bone	
For control/relieve eliminate end points:
 

○ Record changes as new lesions or no new lesions

○ Changes in intensity of uptake alone do not constitute progression or regression

○ First schedule reassessment:

○ No new lesions: continue therapy

○ New lesions: perform a confirmatory scan 6 or more weeks later

○ Confirmatory scan:

○ No new lesions: continue therapy

○ Additional <math>\geq 2</math> new lesions: progression

○ Subsequent scheduled reassessments:

○ No new lesions: continue

○ New lesions: progression

○ For delay/prevent end points (Progression)

○ Exclude pseudo-progression in the absence of symptoms or other signs of progression

○ At least two new lesions on first post-treatment scan, with at least two additional lesions on the next scan (2+2 rule)

○ If at least two additional new lesions are seen on the next (confirmatory) scan, the date of progression is the date of the first post-treatment scan, when the first two new lesions were documented.

	

○ For all scans after the first post-treatment scan, at least two new lesions

○ Date of progression is the date of the scan that first documents the second lesion

Frequency of assessment of bone scan or other CT scans	Every 8 to 9 weeks for the first 24 weeks, then every 12 weeks

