## 12.2 Disease Progression in Soft Tissue Lesions

Patients should be re-evaluated for response/disease progression every 8 weeks for the first 24 weeks, and then every 12 weeks. No confirmatory scan is required for soft tissue lesions following initial documentation of objective response.

Response and progression in soft-tissue lesions will be evaluated in this study using the new international criteria proposed by the revised Response Evaluation Criteria in Solid Tumors (RECIST) guideline (version 1.1) [Eur J Ca 45:228-247, 2009]. Changes in the largest diameter (unidimensional measurement) of the tumor lesions and the shortest diameter in the case of malignant lymph nodes are used in the RECIST criteria.

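### Exactly two new bone lesions on a later scan passes the Section 6.1 retreatment gate as non-progression but is progression under Section 12.1.1

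*Combined protocol and SAP*

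**What the plan says.** Section 6.1 permits retreatment after the two planned cycles. The patient's pain must recur at 4 or above within 6 months after a 16-week pain observation period, and there must be "no disease progression on bone scans". A parenthesis gives the meaning of that phrase as 2 or fewer new bone lesions. Evidence of clinical progression also bars retreatment, and an adverse-event evaluation and organ and marrow criteria apply.

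Section 12.1.1 states which PCWG3 parts apply to this trial. They include the bone criteria for delay/prevent (progression) endpoints. On the first post-treatment scan, two new lesions need confirmation, "with at least two additional lesions on the next scan (2+2 rule"). After that the rule is "For all scans after the first post-treatment scan, at least two new lesions", with no confirmation stated. Progression is dated to the scan on which the second lesion is first documented.

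Section 9.4.8 counts "progression of bone lesions assessed per PCWG3 criteria" as a clinical PFS event.

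The Section 11 retreatment footnote repeats only the pain condition and says nothing about bone scans. Neither 6.1 nor 12.1.1 names the scan against which a lesion is new, and 12.1.1 does not say which scheduled scan is the first post-treatment scan.

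**The concern.** The two sections use the same idea, disease progression on a bone scan, with thresholds that overlap. Section 6.1 treats up to and including two new lesions as non-progression. Section 12.1.1 treats two and above as progression on later scans. A patient at the boundary is therefore progressed for clinical PFS and not progressed for the retreatment decision, on the same images.

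What is at stake is a treatment decision. Two sites with the same scan could re-dose or refuse, and each could cite the protocol. A patient re-dosed in this way would also be described as having no disease progression while the trial's own dataset records a progression event.

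**Working it through.** No sample-size or error-rate arithmetic is involved. The check sets the two rules side by side.

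**Step 1: the rules by count.** Let k be the number of new bone lesions on a scan after the first post-treatment scan, counted from the same reference scan in both sections. Section 6.1 reads non-progression if k ≤ 2. Section 12.1.1 reads progression if k ≥ 2.

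| k | Section 6.1 bone gate | Section 12.1.1 | Agree? |
|---|---|---|---|
| 0 | passes | no progression | yes |
| 1 | passes | no progression | yes |
| 2 | passes | progression | **no** |
| 3 | blocks | progression | yes |
| 4 | blocks | progression | yes |

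With a shared count, the overlap is at k = 2.

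**Step 2: what happens without a shared count.** The table assumes a common reference scan that the plan does not give. Two examples, taking Week 8 as the first post-treatment scan (an assumption), show that other counts can conflict.

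- Three new lesions at Week 8 and none later. Counted from baseline, 6.1 blocks (3 > 2). Under 12.1.1 the two additional lesions never appear, so there is no progression. The sections disagree in the opposite direction.
- One new lesion at Week 16 and one more at Week 24. Because 12.1.1 dates progression to the scan documenting the second lesion, it can be read cumulatively, giving progression at Week 24. Read scan by scan, 6.1 sees one new lesion and passes.

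**Step 3: can a later scan fall in the retreatment period?** Section 12.1.1 sets bone scans at this frequency: "Every 8 to 9 weeks for the first 24 weeks, then every 12 weeks". Using 8-week intervals, as the Section 11 calendar does, the scans fall at Weeks 8, 16, 24, 36 and 48. Take 6 months as 26 weeks (an assumption). The start of the 16-week period is not fixed, so three starts are shown:

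- First dose: Week 16 to 16 + 26 = Week 42.
- Pain index 3 or below first reached at Week 2: 2 + 16 = Week 18 to 18 + 26 = Week 44.
- Reached at Week 12: 12 + 16 = Week 28 to 28 + 26 = 54, capped at the 12-month follow-up, Week 52.

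Scheduled scans inside each window that come after the first post-treatment scan:

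| First post-treatment scan | Weeks 16–42 | Weeks 18–44 | Weeks 28–52 |
|---|---|---|---|
| Week 8 | 16, 24, 36 | 24, 36 | 36, 48 |
| Week 24 (from the calendar's Post-treatment heading) | 36 | 36 | 36, 48 |

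Every combination leaves at least one scheduled scan to which the at-least-two rule applies. This is the schedule only. Footnote g in Section 11 makes follow-up scans subject to clinical indication and institutional standards.

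**Step 4: test of candidate corrections.**

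- Changing 6.1 to fewer than 2 removes the overlap at k = 2 but leaves the second example in Step 2 open.
- Replacing the number with a bare reference to PCWG3 closes both the k = 2 overlap and that example. However, it would admit the first example in Step 2, a patient whom 6.1 counted from baseline now blocks.
- Requiring both conditions closes the overlap and the second example, and for any one reference scan it admits nobody whom 6.1 now blocks, since k < 2 implies k ≤ 2.

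**The case against.** The strongest reply is that 6.1 is a deliberate allowance. This is a palliative trial with a pain endpoint, and re-dosing despite limited radiographic change is a defensible policy. PCWG3 is invoked to measure effect and PFS, and no section says that it governs retreatment. That policy may be what the sponsor wants. But 6.1 offers two or fewer new lesions as the meaning of no progression and states no exception to 12.1.1, so the text does not express an allowance.

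A second reply is that other gates will catch the patient. Retreatment needs recurrent pain, 6.1 also bars clinical progression, and 9.4.8 counts "symptomatic progression (increasing pain from a metastatic lesion") as progression. This stands in part and limits the consequence. It does not settle the matter for a patient whose returning pain is not judged to be clinical progression, and for him the lesion count can decide.

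Three stronger readings are tempting, and the documents do not support them.

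- A reader might infer that two is the only conflicting count. That needs a common reference scan, which neither section names.
- A reader might infer that the Section 6.4 stop list directly contradicts 6.1, because it includes disease progression. That list is written for the initial two cycles, and retreatment has its own sentence there, so it is not clearly a retreatment gate.
- A reader might infer a specific radiation harm. The two extra injections are the ordinary permitted retreatment, and the documents tie no particular harm to giving them at this boundary.

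**Conclusion.** The point holds. On a scan after the first post-treatment scan, exactly two new bone lesions is non-progression for retreatment under 6.1, progression under 12.1.1, and hence a clinical PFS event under 9.4.8. This follows directly from the two texts when the same count is used. Whether other counts conflict depends on the unstated reference scan, so no claim is made that two is the only one.

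The size is modest. The number of patients affected cannot be derived from the documents and may be zero in a trial of 25. The primary endpoint is a pain index and the Simon rule counts sustained pain responders, so neither changes. What is wrong is a treatment threshold as written, and it is worth correcting because it decides whether a patient already recorded as progressed can be re-dosed.

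**What to change.** In Section 6.1, replace the parenthesis with: fewer than 2 new bone lesions, and no bone progression per Section 12.1.1, counted from the same reference scan as Section 12.1.1. Repeat this in the Section 11 retreatment footnote. Since 12.1.1 does not name that scan, add one sentence there identifying the first post-treatment scan and the comparator for new lesions. If sites now count from baseline, choosing a later comparator could lower the count for some patients, so the choice should be deliberate.

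The cost is a few lines of text, with no change to sample size, visits or analyses. The clinical downside is that patients with exactly two new lesions lose access to retreatment, including those with two unconfirmed lesions on the first post-treatment scan. If the sponsor intends to re-dose patients with two new lesions, 6.1 should state this as an explicit exception to PCWG3 progression and not describe it as absence of progression.
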